Noninvasive Electrical Stimulator as an Adjunct for Pain Control After Ureteroscopic Stone Management

Study Protocol and Statistical Analysis Plan

NCT05153629

September 19, 2022

Study Title:

Treatment of Ureteral Stent Pain with a Transcutaneous Electrical Nerve Stimulator (TENS for US)

Principal Investigator: [name]

Co-Investigators: [name], [name], [name]

Sponsor or funding source: Urology Department

Background:

Ureteral stent placement is one the most common and frequent procedures performed post-ureteroscopy.⁵ A double J-stent is the common type of stent used during the ureteral stent placement procedure. The 'pigtail' design of the stent prevents it from migration. Although there is no clinical evidence why stenting is required, but many studies indicate a few reasons why stenting might be required, and this includes ureteral dilation, trauma to ureter due to constant in and out of the ureter during ureteroscopy, leaving behind large stone fragments, impacted stone, misfiring of laser during ureteroscopy etc.^{1,2,3} The stent is used to maintain the ureter patency, recovery and/or prevent obstruction due to inflammation caused during the ureteroscopy procedure. The stent is typically removed after 3-7 days, a duration long enough for the ureter to heal itself from the trauma caused by the ureteroscopy procedure.⁶

Despite the benefits of placing a stent post-ureteroscopy, eighty percent of patients with ureteral stents complain of a various side effect from the stent with the most common complaint being lower back pain. This pain is thought to occur through the same mechanism of action i.e., back pressure into the renal pelvis, as an obstructed kidney stone.^{4,5} The ureteral stent keeps the ureter open and the urine flows through this stent in both directions i.e., towards the bladder or back to the kidney due to it being an open tube. When the urine flows back to the kidney due to pressure in the bladder, it creates the same back pressure as an obstructing stone in the ureter, and results in similar lower back pain that can be as severe as the pain with an obstructed stone.

To manage the pain and discomfort associated with the ureteral stent, some physicians will prescribe pain medications, such as Tylenol, Motrin, NSAIDs, or Opioids. Patients will fall back to any of these pain management medications, specifically Opioids, when their pain is intolerable. Opioid addiction is an epidemic in US, there are numerous initiatives to curb this crisis starting from limiting the number of opioid prescriptions.

In an effort to find new and alternative ways of treating this pain, we are conducting a study on Transcutaneous Electrical Nerve Stimulation (TENS) to measure its effect on reducing the pain caused by ureteral stents and compare it to the standard of care practice that does include various pain management medications.

In this study, the team is proposing to recruit 60 patients who underwent a kidney stone procedure with a post procedural ureteral stent. Thirty of the sixty patients will be randomized

and discharged with a TENS device (treatment group) that they will use over a course of 3-7 days (typical duration of a stent in the patient) to see how the device helps in treating their pain associated with the stent. The electrode pad will be applied to the lower back near the paravertebral position and the site of pain (Figure 3). The remaining 30 randomized patients will be in the control group, and will not receive a TENS device. All 60 patients are required to complete a daily pain visual analog score (VAS) score along with their daily pain medication intake. Once the stent is removed in the physician's clinic during their follow up visit, they will hand over the TENS and complete a survey of their experience and pain score with the device. These survey results from the treatment group will be compared against the control group to measure efficacy and safety of the TENS device for treating renal colic pain.

The study will not otherwise affect the care a patient will receive. The TENS group will receive the same standard of care treatment as the non-TENS group, but the TENS group are asked to use the TENS device 4 times a day for 60 minutes during each treatment while they have the ureteral stent placed in their body.

Objectives:

- 1) Primary outcome – To determine the patient with the TENS unit had a lower reported pain and nausea VAS score compared to control (non-TENS) group
- 2) Secondary outcome – To determine the patient with the TENS unit took less number of opioids during the duration of stent placed in their ureter compared to control (non-TENS) group

Methods and Measures

This will be a randomized control trial with subjects randomized to either the standard of care pain-relief group or an FDA-cleared TENS unit. The TENS group will follow the standard of care pain-relief group if they are intolerance to TENS or they are seeing no benefits from the TENS unit during the duration of the study. If they stop using TENS or continue following the standard of care treatment intervention, they will document such in the daily survey form.

Participants will be enrolled when they are seen in the Urology clinic for their ureteroscopy procedure scheduling. Participants with kidney stones who are consented for a ureteroscopy will be eligible for the study. Participants will be informed during the enrollment and consent process that if they decide to participate in the study, they will be randomized to receive a TENS unit or the typical standard of care treatment. They can elect to decline the enrollment based on that information, or if they choose to enroll, then they will sign the consent form for participating in the study.

Randomization participants using random generator will be performed by the urology physicians or residents in the preop area of the [name] hospital. The patient will be notified in the preop are which study group they are being assigned to, and they will be given further instructions and training post-ureteroscopy procedure in the PACU area. TENS group will be discharged with a TENS unit along with training and instructions on how to use the device. All participants will be instructed to complete a daily survey at the end of day and a final

survey at the time of stent removal. All follow up care will be performed remotely. Participants enrolled in the TENS group will return their TENS unit during the stent removal in the physician's office.

The device settings will be adjusted beforehand and will be the same for every participant, unless it is felt to be too strong, in which case a lower intensity (current intensity with no changes to other stimulation parameters) setting will be used. It should cause no more than minimal tingling to the area on the back where it is applied. The placement of electrode pads will be determined in the PACU area post-ureteroscopy, and the participants will be trained to the device settings and electrode pad placement.

Participant Selection Criteria:

Inclusion

- Adult patients undergoing standard of care ureteroscopy and laser lithotripsy for urinary stone disease
- Patients receiving a stent following their ureteroscopy and laser lithotripsy

Exclusion

- Children
- Pregnant patients
- Patients unable to answer pain questionnaire
- Patients undergoing PCNL
- Patients being treated for Urologic malignancy with ureteroscopy
- Patients who require long term or chronic ureteral stent management
- Patient with implantable stimulators
- Patient with epilepsy
- Patients undergoing laser lithotripsy without stent placement

Sample Size

60 participants with 30 participants in each group

Outcome Measures:

Primary outcome will be to measure and compare daily pain score on a VAS 11-point scale in the TENS group vs control group. Secondary outcome will be the amount of pain medication used in TENS group vs the control group.

Statistical Plan:

The two groups will be analyzed using t-tests or ANOVA, and the final results will be analyzed using descriptive analytics. A regression analysis will be performed for independent outcome prediction.

Recruitment Methods and Consent

All participants will be recruited during their outpatient consultation for kidney stones with the urology clinic. Participants who are scheduled for a standard ureteroscopy procedure with laser

are eligible for the study and they will be informed about the study. The consent form will be shared by the attending physician to the participant during their initial consultation visit and the participants will have sufficient time to make a decision if they want to participate or not. Signed informed consent form will be obtained for each participant before their ureteroscopy procedure.

Reporting of Adverse Events or Deviations

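### The opioid outcome rests on an unverified diary kept by patients who know their arm; a tablet count at stent removal would be a cheap check

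*Combined protocol and SAP*

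**What the plan says.** - **Source of the data (Background).** "All 60 patients are required to complete a daily pain visual analog score (VAS) score along with their daily pain medication intake". Methods and Measures gives the same end-of-day form to both arms: "All participants will be instructed to complete a daily survey at the end of day and a final" survey when the stent comes out.
- **Outcome.** The second item under Objectives is whether TENS patients "took less number of opioids during the duration of stent placed in their ureter compared to control (non-TENS) group". Outcome Measures words it differently: "Secondary outcome will be the amount of pain medication used in TENS group vs the control group".
- **Knowledge of arm.** Methods and Measures: "The patient will be notified in the preop are which study group they are being assigned to". Background: "The remaining 30 randomized patients will be in the control group, and will not receive a TENS device". No sham is described.
- **Contact at the end.** Background: "Once the stent is removed in the physician's clinic during their follow up visit, they will hand over the TENS and complete a survey". Methods and Measures makes follow-up care remote, but places stent removal in the physician's office. The TENS unit is the only item to be returned there. No tablet count, prescription record or other check on intake is described.
- **A request to TENS patients only (Methods and Measures).** "If they stop using TENS or continue following the standard of care treatment intervention, they will document such in the daily survey form".

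**The concern.** Pain can only be reported by the patient, but opioid tablets can be counted. The Background motivates the trial partly by the opioid problem, so a finding of fewer opioids with TENS would be prominent among its results. As planned, that finding would depend entirely on what unblinded patients write down at home. A patient given a device may record tablets more or less completely than a patient given none. Fewer tablets recorded then looks the same as fewer tablets taken, and no analysis of the diary can separate the two. Depending on the direction, the trial could report opioid sparing that did not happen or miss sparing that did.

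**Working it through.** **The plan's own figures.** The Sample Size section gives 60 patients, 30 per arm, and the Statistical Plan names t-tests or ANOVA. The documents give no alpha, power, effect size, SD or expected opioid use. There is therefore no opioid figure to reproduce, and what follows is an illustration.

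**Inputs**
- From the documents: n = 30 per arm and a t-test, so 58 degrees of freedom.
- Assumed: two-sided alpha 0.05, control mean 5.6 tablets, SD 7 to 9, and a fraction u of tablets left unrecorded in one arm only.

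**Case 1: no true effect, TENS arm under-records by u.**
Apparent difference = u × 5.6. Shift in SD units d = u × 5.6 / SD. Noncentrality = d × √(30/2). The table gives the chance that the t-test is significant in favour of TENS (2.5% at u = 0).

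| u | Apparent difference | d at SD 9 | d at SD 7 | Chance at SD 9 | Chance at SD 7 |
|---|---|---|---|---|---|
| 10% | 0.56 | 0.06 | 0.08 | 4.2% | 4.9% |
| 20% | 1.12 | 0.12 | 0.16 | 6.9% | 8.8% |
| 40% | 2.24 | 0.25 | 0.32 | 15.6% | 22.9% |

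This treats under-recording as a pure shift with equal SDs. A simulation with skewed counts of the same mean and SDs, deleting tablets at random in the TENS arm, gave about 6% to 9% at u = 20% and 18% to 30% at u = 40%. The shift model is adequate at 20% and somewhat low at 40%.

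**Sensitivity to the assumed spread.** The SDs above are 7/5.6 = 1.25 and 9/5.6 = 1.61 times the mean. With the normal approximation, the chance at u = 20% is 7.4% if the SD is 1.5 times the mean, 11.8% if equal to it, 17.7% at 0.75 times and 34.1% at 0.5 times. At u = 10% the same four values are 4.4%, 5.8%, 7.4% and 11.8%. The result depends strongly on a spread that the documents do not give.

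**Case 2: control arm under-records by u, TENS arm records fully.**
With a true reduction of 30%, the apparent reduction is 1 − 0.70/(1 − u). At u = 20% this is 1 − 0.70/0.80 = 12.5%. At u = 30% it is 1 − 0.70/0.70 = 0. The same mechanism in the other arm therefore shrinks or removes a real effect.

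**What the TENS-only request shows about direction.** The Background requires the intake record of all 60 patients, so the outcome item is common to both arms. The extra sentence in Methods and Measures asks TENS patients for their treatment status: whether they stopped the device or continued standard care. It does not replace the medication record. An added prompt could make TENS patients' recording more complete as easily as less complete. The daily form is not reproduced, so its wording cannot be judged.

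**The case against.** The strongest reply is that self-recorded intake is a reasonable choice for a secondary outcome in a 60-patient, department-funded trial. The diary covers non-opioid drugs and gives day-by-day timing, and a count of opioid tablets does neither. This stands, and is why the diary should be kept.

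A count is also not fully objective. Patients who know their arm bring the container, and tablets discarded, given away or taken from an earlier supply make dispensed minus remaining wrong. Only TENS patients otherwise have something to bring back, so container return could itself differ by arm. These limits are real. The same reminder to both arms and a report of missing counts by arm address the last one. The others remain, but a count still does not depend on what the patient chose to write down.

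The size is assumed throughout, and under-recording of 10% with widely spread counts adds little to the 2.5% base rate. That also stands.

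A reader might infer that the TENS-only request casts medication as a departure from the device and so discourages TENS patients from recording it. The documents do not support this. The request concerns treatment status, the Background says TENS patients receive the same standard care as controls, and the intake record is required equally of both arms.

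**Conclusion.** The point holds as a weakness in measurement whose direction is unknown. Opioid intake is known only from an unverified, open-label self-report, and a check is available at a visit that already takes place. Unequal recording could create or hide a difference.

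Under the stated assumptions the risk is small at 10% one-sided under-recording, moderate at 20% and substantial at 40%. None of those fractions, nor the mean and SD, comes from the documents. It would go too far to conclude that the plan is biased towards opioid sparing, or that the two arms answer different medication questions.

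The two wordings of the secondary outcome also matter here: a tablet count measures the number of opioids under Objectives, but not the total pain medication under Outcome Measures. Overall this is a cheap improvement.

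**What to change.** 1. At the stent-removal visit, record opioid tablets dispensed and remaining for every patient in both arms. Give both arms the same reminder to bring the container, and confirm that control patients also attend in person.
2. Use dispensed minus remaining as the measure for the opioid outcome. Report the number of missing counts by arm. Use the diary total where the container is missing, and for all patients as a sensitivity analysis.
3. Keep the diary for non-opioid medication and daily timing. Use one identical medication question in both arms, and put stopping TENS in a separate TENS-only item.
4. Reconcile the secondary outcome under Objectives (number of opioids) with that under Outcome Measures (amount of pain medication), and state that the count serves the opioid outcome.

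Cost: a line in the discharge instructions, a line on the removal-visit form and about a minute per patient. Some containers will be forgotten, so the outcome will mix two sources for those patients, and a count cannot detect tablets discarded, shared or taken from an earlier supply.

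### Patients are randomised and told their arm in preop, before the stent criteria can be confirmed, so a patient left without a stent is excluded after the arm is known (minor)

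*Combined protocol and SAP*

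**What the plan says.** All places are in the combined protocol and SAP.

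- **Timing of allocation (Methods and Measures).** "Randomization participants using random generator will be performed by the urology physicians or residents in the preop area". On disclosure: "The patient will be notified in the preop are which study group they are being assigned to". Device training follows in the PACU after ureteroscopy, and the electrode position is also settled there.
- **Formal criteria (Participant Selection Criteria).** Inclusion: "Patients receiving a stent following their ureteroscopy and laser lithotripsy". Exclusion: "Patients undergoing laser lithotripsy without stent placement".
- **Recruitment statements.** Methods and Measures: "Participants with kidney stones who are consented for a ureteroscopy will be eligible for the study". Recruitment Methods and Consent likewise treats as eligible "Participants who are scheduled for a standard ureteroscopy procedure with laser". Neither carries a stent condition.
- **Who the 60 are.** The study overview in the Background describes them as people who have already had the procedure and have a stent. Sample Size says only "60 participants with 30 participants in each group".
- **Reasons for stenting (Background).** Some arise during surgery (trauma to the ureter, fragments left behind, laser misfiring). Others, such as an impacted stone, may be known earlier. The same section calls stenting one of the most common procedures after ureteroscopy. It does not say when the decision is made.
- **Analysis and follow-up.** The Statistical Plan names t-tests or ANOVA and a regression, but no analysis population. The last assessment is a final "survey at the time of stent removal".

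**The concern.** Eligibility is normally settled before allocation, so that everyone randomised belongs to the trial population. Here one criterion is an event that follows allocation and disclosure. A patient who leaves theatre without a stent has been randomised, knows the arm, and then fails the criteria.

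Two things are at stake. First, exclusions made after the arm is known can make the analysed groups differ if the chance of being stented depends on the arm. The documents conceal the arm from nobody, including whoever decides on the stent. Second, the 60 is ambiguous: it may count randomised or stented patients. On the first reading, fewer than 30 per group may be evaluable.

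**Working it through.** **The plan's own figure.** The 30 per group cannot be reproduced, because the documents give no alpha, power, effect size, SD or dropout. Two-sided alpha 0.05 and 80% power are assumed below. The share u of randomised patients left without a stent is also an assumption.

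**1. The order of events.**

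| Step | Where stated | When |
|---|---|---|
| Consent | Recruitment Methods and Consent | before ureteroscopy |
| Randomisation and disclosure | Methods and Measures | preop |
| Stent placed or not | Participant Selection Criteria | after ureteroscopy |
| Pad placement and training | Methods and Measures | PACU |

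The stent criteria come after allocation. The overview in the Background, where the 60 already have a stent, fits the criteria but not the preop allocation.

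**2. Could such an exclusion occur?** P(at least one of 60) = 1 − (1 − u)^60.

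| u | Expected number | P(at least one) |
|---|---|---|
| 0% | 0 | 0 |
| 1% | 0.6 | 1 − 0.99^60 = 45% |
| 5% | 3 | 1 − 0.95^60 = 95% |
| 10% | 6 | 1 − 0.90^60 = 99.8% |

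The chance passes one half at u = 1 − 0.5^(1/60) = 1.15%, that is, about 1.2%.

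**3. Power, if 60 counts everyone randomised.** Two-sample t-test, noncentral t. The reference difference is 0.736 SD, which 30 per arm detects with 80% power.

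- *Dropped:* n per arm = 30(1 − u).
- *Kept:* n stays 30 and the mean difference becomes 0.736(1 − u). This assumes no effect in unstented patients and an unchanged SD.

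| u | n per arm, dropped | Detectable difference, dropped | Power, dropped | Diluted difference, kept | Power, kept |
|---|---|---|---|---|---|
| 0% | 30 | 0.736 SD | 80% | 0.736 SD | 80% |
| 5% | 28.5 | 0.755 SD | 78% | 0.699 SD | 76% |
| 10% | 27 | 0.777 SD | 76% | 0.662 SD | 71% |

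If 60 counts stented patients, dropping the others costs no power.

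**4. Hypothetical bias.** Suppose a patient is stented when latent procedural trauma exceeds a threshold c, and trauma correlates r with later pain. With a proportion p stented, the mean pain of stented patients shifts by r·φ(c)/p SD, where φ is the standard normal density. Assume 95% stented in one arm and 90% in the other.

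- φ(c) = 0.1031 at 95% and 0.1755 at 90%.
- r = 0.3: 0.3 × (0.1755/0.90 − 0.1031/0.95) = 0.0585 − 0.0326 = 0.026 SD.
- r = 0.5: 0.0975 − 0.0543 = 0.043 SD.
- Standard error = √(1/28.5 + 1/27) = 0.269 SD, so the bias is 0.10 to 0.16 standard errors. Type I error is 5.1% to 5.3%.
- If stenting itself correlates only 0.5 with trauma, the bias halves to 0.013 to 0.022 SD (type I error 5.0% to 5.1%).
- Equal stenting in both arms gives zero bias in this model.

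**5. Consents needed for 60 stented patients.** On average 60/0.95 = 63.2 or 60/0.90 = 66.7. The smallest number giving at least a 90% chance is 66 at 5% unstented (probability 0.954) and 70 at 10% (0.913).

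**The case against.** The best defence is that the documents already imply what happens to an unstented patient. The criteria exclude lithotripsy without a stent, and the overview describes 60 stented patients. Device use, opioid counting and the final survey are all tied to the time the stent is in place. **This largely stands.** A reader might infer that the plan leaves the fate of such a patient wholly open. It does not: exclusion is the evident reading, and an excluded patient needs no final assessment. On its own, the missing sentence on replacement and reporting would be a missing detail.

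The recruitment sentences can also fairly be read as describing the pool from which patients are drawn, and consent before a criterion is confirmed is ordinary practice. That stands too. It does not excuse randomising and disclosing before the criterion is confirmed.

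Two stronger readings are tempting and unsupported.

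- *Post-allocation exclusions are very likely.* That holds only if roughly 5% to 10% go unstented. The documents give no rate, and stents may often be planned in advance.
- *The comparison is biased.* The documents give no evidence that stenting depends on the arm, and no reason why a device worn on the back would change that decision. They do not say that the person who randomises also decides on the stent. The Background says care is not otherwise affected. That is an intention and conceals nothing, but it points away from bias.

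What survives is the order of events: the plan as written excludes after allocation, with the arm unconcealed, when a small change would avoid this.

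**Conclusion.** The point holds as a minor one. Allocation and disclosure precede an eligibility criterion that only the procedure can settle, and the account of the 60 in the Background does not fit that order.

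Exclusions after the arm is known may occur, and are more likely than not once about 1.2% of patients go unstented. The power loss is 2 to 4 percentage points if 5% to 10% are dropped, and about 4 to 9 if they are kept. It applies to dropping only if 60 counts everyone randomised. The bias of about 0.01 to 0.04 SD is hypothetical and rests on one assumed contrast in stenting, 95% against 90%.

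Confidence is high on what the text says and low on the size of the consequence. The case for change is that it is cheap and removes the post-allocation stent exclusion, not that large harm is expected.

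**What to change.** Reconcile the Background overview, Methods and Measures, and Participant Selection Criteria on one order.

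- **Preferred.** Keep pre-operative consent. Randomise and disclose the arm in the PACU once stent placement is recorded, before the training already done there, from a concealed computer-generated list. Define the 60 as patients randomised after stent placement. Report how many consented patients were not randomised because no stent was placed.
- **If randomisation stays in preop.** Conceal the arm until stent status is recorded. State in advance that patients left without a stent are excluded from the primary comparison and replaced, and report their number by arm.

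**Cost.** A protocol and IRB amendment; someone to prepare and hold the list; a device on hand in the PACU. More than 60 patients must be consented: about 66 to 70 at an assumed 5% to 10% unstented, for at least a 90% chance of 60 stented patients. Under either option patients no longer learn their arm before the procedure, and the sponsor should weigh that loss. The documents do not say whether PACU staff could take on randomisation. No extra visit or procedure is needed.

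No view is taken on when a stent should be placed.

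### Allocation is opened in preop, analgesic supply is neither fixed nor recorded, and so fewer opioids in the TENS arm could partly reflect prescribing, with no means of checking

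*Combined protocol and SAP*

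**What the plan says.** **Order of events (Methods and Measures).** "Randomization participants using random generator will be performed by the urology physicians or residents in the preop area". At that point, "The patient will be notified in the preop are which study group they are being assigned to". After the procedure, "they will be given further instructions and training post-ureteroscopy procedure in the PACU area". Then "TENS group will be discharged with a TENS unit along with training and instructions on how to use the device". No sham device or blinding is described.

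**Analgesic care.** The Background describes the management of stent pain in general terms: "some physicians will prescribe pain medications, such as Tylenol, Motrin, NSAIDs, or Opioids". It commits the trial to equal care, "The TENS group will receive the same standard of care treatment as the non-TENS group", and the sentence before that one says the study leaves a patient's care otherwise unchanged. No discharge regimen, quantity or repeat-prescription rule is given.

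Methods and Measures describes the arms differently. Subjects are allocated to standard pain relief or to a TENS unit, and TENS patients are to follow the standard pain-relief group if they cannot tolerate the device or see no benefit from it.

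**Outcome and data.** The second objective is that TENS patients "took less number of opioids during the duration of stent placed in their ureter". Under Outcome Measures the wording is broader: "Secondary outcome will be the amount of pain medication used in TENS group vs the control group". The Background lists daily pain scores and daily medication intake as collected. The amount prescribed or dispensed is not listed. The Statistical Plan names t-tests or ANOVA and a regression whose covariates are not given.

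**The concern.** A patient cannot take opioids from a discharge prescription that was not written, so the opioid count depends on supply as well as on need. If those who decide supply know the arm, supply can differ by arm for reasons unrelated to pain relief. A prescriber might, for instance, think a patient going home with a device needs a smaller prescription. The TENS arm would then record fewer opioids even if TENS did nothing.

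At stake is the interpretation of the secondary result. The trial could report an opioid saving and be unable to say how much of it came from the device. Because only intake is listed as collected, the question could not be settled afterwards. The problem is separate from whether every randomised patient receives a stent; it would remain if all of them did.

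**Working it through.** The plan has no figure of its own to reproduce here. The check has two parts: what the text establishes, and how large the effect could be under stated assumptions.

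**1. The links in the chain**

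| Link | Basis | Status |
|---|---|---|
| Urology physicians or residents randomise and the patient is told in preop | Methods and Measures | Stated |
| Procedure, PACU training and discharge come later | Methods and Measures | Stated |
| Discharge analgesics are prescribed after the arm is known, by someone who knows it | Order of events and who randomises | Inferred; prescriber and timing not given |
| Drug and quantity are open | Background names a range of drugs; no regimen anywhere | Stated by omission |
| Equal care in both arms | Background | Stated, but no content or check; Methods and Measures pulls against it |
| Supply is recorded | Only daily intake is listed | Not listed |

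**2. Arithmetic on assumed supply.** The documents give no prescribing rate. Assume 80% of controls are supplied opioids, those supplied use 10 units on average, and TENS has no effect. Mean use = share supplied × 10.

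- Control: 0.80 × 10 = 8 units.
- TENS at 70%: 7 units, apparent saving 1/8 = 12.5%.
- TENS at 60%: 6 units, 2/8 = 25%.
- TENS at 50%: 5 units, 3/8 = 37.5%.

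This treats patients who go without as average users. Suppose instead that they would have used half the average (5 units). At 60% supply the loss is then 0.20 × 5 = 1 unit, and the apparent saving is 1/8 = 12.5% rather than 25%.

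**3. How often this alone would give a significant result.** Inputs: 30 per arm (Sample Size), a t-test (Statistical Plan), and an assumed two-sided 5% level. There were 20,000 simulated trials per row, with no TENS effect and 80% of controls supplied. The last two columns give the share of trials significant in favour of TENS.

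| TENS supplied | Use if supplied: mean 5, SD 4 | Use if supplied: mean 10, SD 5 |
|---|---|---|
| 80% | 2% | 2% |
| 70% | 7% | 9% |
| 60% | 16% | about 24% |
| 50% | 31% | about 48% |
| 40% | 54% | 72% |

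Cross-check of the 60% row, mean 5 and SD 4. With share p supplied, the variance is p(16 + 25) − (5p)².

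- Control: 0.8 × 41 − 16 = 16.8.
- TENS: 0.6 × 41 − 9 = 15.6.
- Pooled SD: √16.2 = 4.02.
- Difference in means: 4.0 − 3.0 = 1.0, which is 0.25 SD.
- Power for a 0.25 SD shift with 30 per arm: 16%, in agreement with the table.

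**4. Direction.** For opioids, lighter prescribing to TENS patients favours TENS. For all pain medication, patients given fewer opioids may take more of the other drugs, so the direction is uncertain. For pain scores, a bias against TENS would require total analgesia to fall, which nothing in the documents shows.

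**The case against.** The strongest reply is that the key link is not in the text. The plan does not say who writes the discharge prescription or when. It could be ordered at the clinic visit, or come from a standard set. This stands: the point is a risk that follows from the described sequence, and if prescriptions already precede randomisation, the protocol need only say so.

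A second reply is that the Background commits to equal care and to leaving care otherwise unchanged. Arm-driven prescribing would breach that commitment, and deviations must be reported. This stands in part. It is a commitment, but with no drug, quantity or supply record a breach would be hard to see. The fallback wording in Methods and Measures also makes it unclear what equal care means.

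Two stronger readings are tempting and not supported. A reader might infer that the trial's declared purpose is to limit opioid prescriptions, so that its physicians would be expected to hold them back in the TENS arm. The Background mentions such limits as outside initiatives; the stated purpose is to find other ways of treating the pain. A reader might also infer that only some of this trial's physicians prescribe analgesics. That sentence describes general practice, and the comparator is said to include various pain medications.

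Finally, every supply figure above is assumed, and small differences in supply do little harm: about 7% to 9% of null trials at 70% supply, against 2% with equal supply. That also stands.

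**Conclusion.** The concern holds as a risk of bias to the secondary outcome, at medium confidence. The sequence allows the arm to be known before analgesics are prescribed, the promise of equal care has no defined content, and supply is not listed as collected. Fewer opioids in the TENS arm could therefore partly reflect prescribing, and the planned data could not confirm or exclude it. The documents do not show that prescribing would differ by arm or that bias occurred.

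The size is unknown. On the assumptions above, supply of 50% to 70% in the TENS arm against 80% in controls gives an apparent opioid saving of 12.5% to 37.5% with no device effect, and less if opioids are withheld mainly from patients who would have used few. The change is worth making because it is cheap and because supply data that were not collected may not be recoverable later.

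**What to change.** 1. Under Methods and Measures, change the order of events: the discharge analgesic prescription is signed first, and the allocation is then opened and disclosed in the PACU. Device training and pad placement already take place there, so no added staff or visit is needed. The choice of medicines stays with the physician.
2. Record the quantity of opioid and of other analgesics supplied to each patient, including any later prescription while the stent is in place. The new sequence cannot cover later prescriptions, because follow-up care is remote and the arm may be known by then; the supply record has to.
3. Report supply by arm next to the secondary outcome.
4. Reconcile the equal-care statement in the Background with the either/or and fallback wording in Methods and Measures, and reconcile the two wordings of the secondary outcome (opioids in Objectives, pain medication in Outcome Measures).

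Cost: a revised description of when allocation is opened and when patients are told, one more item on the data form, and one table. The downside is that patients learn their arm in the PACU rather than in preop.
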